**Question 3: What are the barriers and facilitators of intervention implementation?**

**Analyses.** For process data on fidelity, we conduct descriptive statistics and summary analysis on the *rigor of the intervention* implementation to the standardized manualized protocol through fidelity data. For in-depth interviews, we conduct ongoing saturation analyses, based on iterative coding during data collection. Each audio recording is transcribed word-for-word and if need be, translated. Transcriptions are checked for accuracy and entered into NVivo. We also enter all observational notes as memos. We analyze interviews using iterative analyses including qualitative research techniques of open and axial coding. Our investigative team will read with a subset of transcripts co-code with discussions to reconcile differences in coding. Iterative analysis helps to develop initial codebook, which is finalized after data collection ends. Codes are grouped into themes and reviewed by the investigative team.

**COVID-19 Analyses.** We will analyze trial arms to see if there are any differences in main outcomes for the control versus intervention arm during the COVID-19 crisis. We will also examine whether COVID-19 has impacted our main outcomes as compared to other periods of the trial.

**D. POSSIBLE RISKS AND ANTICIPATED BENEFITS AND PRIVACY AND CONFIDENTIALITY**

**1. Potential Risks and Discomforts to Participants**

This research includes a number of potential risks which we outline below. We details procedures to minimize these risks.

- 1) **Biological specimen collection.** We have carefully considered availability of procedures for age-appropriate biologically verified HIV and STIs. We have sought out the latest available but least invasive methods based on preparatory research of available test kits, assays, lab space, and pricing. As such, we have chosen HIV tests (dried blood spot) which are consistent with what is being done for this age group at clinics and urine tests for STIs (Chlamydia trachomatis and Neisseria gonorrhoeae using Xpert CT/NG assays). We use trained and certified counselors, clinic and lab teams to gather HIV/STI biological data and to conduct referrals for confirmatory testing and treatment.
- 2) **Sensitive Information.** Participants may feel uncomfortable with the sensitive nature of some of the survey and/or interviews or research staff/counselor's questions. For example, we ask about sexual and reproductive health questions and about mental health. To minimize discomfort, we use a highly trained team (hiring from our pilot study team) who have experience conducting research with families. We also use a computerized mobile smartphone to collect data, which offers privacy both visually and in regards to sound in our deployment of Audio Computer-Assisted Self-Interviewing Software (ACASI) for sensitive questions to limit social desirability bias in participant reporting of data. ACASI procedures will be suspended for phone based data collection during the COVID-19 crisis. The scientific team will train and supervise the RAs in these procedures and techniques to gather data

sensitively. If any such moments of sensitivity occur during the study, the M-PIs will be available for consultation. Further, if participants experience discomfort, they will be given the option of taking a break, or rescheduling. Further, any distress will be minimized by assurances that participants can refuse to provide any data and that they can withdraw from the study at any time without penalty.

- 3) ***STIs and HIV testing.*** There is a risk of potential anxiety over being tested for HIV/STIs and special considerations for distress and behavioral changes after testing given our target age group (adolescents 14-16 will engage in biologically verified HIV/STIs). South Africa allows for independent consent of HIV testing to be done at age 12 (our eligibility age is 14-16 years, inclusive). South Africa also allows children to independently consent to medical treatment including pregnancy, HIV testing and use of contraceptives. We follow these ethical and legal norms (which also apply to prevention trials) which include trained pre- and post-test counseling by our trained team (at Desmond Tutu HIV Foundation). This pre- and post-test counseling is critical to ensure that: we address pre-test anxiety; we limit any false sense of protection from acquiring HIV and other STI infections that can lead to lead to risk-behavior disinhibition; and that we limit distress upon HIV and/or other STI diagnosis. In addition, we spend significant time during both parent and adolescent consent and assent procedures outlining who, how, and why confidentiality would be breached. We safeguard our participants' confidentiality and privacy. We also explain during the consent and assent under what circumstances mandatory reporting is required. It is also made clear in the consent that health information which is considered private information regarding the adolescent; We explain that adolescents have a right to keep their health information including any HIV and/or STI diagnosis confidential (including from parents), although we will encourage them to disclose HIV and/or STI status and other serious health concerns to a trusted adult in a reasonable time frame (e.g. 3 months) as has been written about by South African researchers and ethicists. We make clear to parents that we will *not* disclose their adolescents HIV and/or STI status or other health information under any circumstance to them or others (aside from the clinic for referral and treatment based on permission of adolescents). We clarify other circumstances in which confidentiality can be breached under pre-specified conditions and to who (such as cases of self or other harm and the legally mandated reporting requirements for disclosure of such information).
- 4) There is a small risk of ***loss of privacy or confidentiality of data***, including sensitive data on sexual behaviors, substance use, and psychological characteristics. We take this risk seriously, and we will take steps to protect participants' confidential data and anonymity. We will ensure that personal identifiers are never included in any research or analytical datasets, or any publications arising from the study. The informed consent documents will bring confidentiality risks to participants' attention and situations under which disclosure can occur (and to who). Names and any other specific personal identifiers will not be included in any datasets: only a unique participant RIN. Tracking information (including names and telephone numbers) will be available solely to the project staff in charge of planning and organizing follow-up visits. We explain the extensive data protections put into place for our data above (see Data Collection, Management, and Protections). The informed consent and assent documents will highlight confidentiality risks.
- 5) This is *not a treatment study* and as such, does not enroll psychiatric patients. Instead we focus on individuals that are not meeting clinically significant levels of depressive symptomology based on self-report because this behavioral intervention has a preventive focus. *Our study is focused on depression prevention.* We conduct a 'selective' preventive intervention where we are selecting for adolescents at elevated risk for depression onset. We use self-report and non-clinician administered measures to assess possible depressive symptoms (using the Center for Epidemiologic Studies Depression Scale – Revised (version for adults and children, a validated and reliable depressive symptom measure in South Africa),

and as such we are not diagnosing mental illness. However we acknowledge that participants may experience *psychological decompensation*. If this occurs, they will be withdrawn from our prevention focused trial. For these participants, we will provide a list of clinics where individuals who meet clinically significant levels of depressive symptomology based on self-report so they can be evaluated by mental health professionals. The target population is served by South Africa's public health system, where services are provided for free at point of service.

- 6) Participants may experience *stigma or discrimination* due to HIV and/or STI status and mental health. We take this risk very seriously. We have taken steps to minimize the risk that participants' HIV/STI status may be revealed due to association with our pilot study (through careful discussion of testing decisions for adolescents in our trial, and careful discussion of confidentiality with both parents and adolescents as explained above). We also put in place data handling, storage, and analysis practices to protect participants' anonymity. We will provide training for all project staff on the needs and strategies for maximizing participants' anonymity. Our Community Advisory Boards will also advise us on how to minimize social harms to participants due to stigma and discrimination.
- 7) *No increases in risk:* No subject will be "enticed" to engage in additional risk to become a participant. We implement consent and assent procedures that build in time for consideration of benefits and harms, and in a proactive engaging discussion of consent and assent considerations that explicitly avoids a "pro-trial enrollment" position.

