- 2) concurs that the adult identified is their parent (to also include primary caregivers in the parental role);
- 3) when more than one child in the family falls within the eligible age range, one child will be chosen at random;
- 4) lives in the household at least 4 days a week; and
- 5) sub threshold depressive symptoms (score 6-15) using the CES-DC (child version).

Adolescents will be excluded if:

- 1) they report no or low symptoms (<6) or clinically significant thresholds of depression (16+);
- 2) If any or both in the adolescent-parent dyad are unwilling to consent and/or assent.

Parent inclusion criteria are:

- 1) 18+ years,
- 2) parent or equivalent person responsible (as identified by the household);
- 3) when more than one parent who provides primary care exists in the household, one will be chosen at random to ensure consistency in intervention activities;
- 4) lives in the household at least 4 days a week; and
- 5) sub threshold depressive symptoms (score 0-15) using the CES-D Revised (adult version).

Parents will be excluded if:

- 1) they report clinically significant thresholds of depression (16+);
- 2) If any or both in the adolescent-parent dyad are unwilling to consent and/or assent.

We do not exclude participants based on ethnicity, population, or language groups, but expect that due to the demographics of our study area, we are likely to enroll predominantly isiXhosa, Black African participants. For adolescents, our intervention focuses on preventing HIV risk behavior so adolescents can be sexually active or inactive. We would also like to clarify that our study is not a treatment study and as such, does not enroll psychiatric patients. Instead we focus on individuals that are not meeting clinically significant levels of depressive symptomology based on self-report because this behavioral intervention has a preventive focus. Because we use self-report and non-clinician administered measures to assess possible depressive symptoms, and as such we are not diagnosing mental illness, we will provide a list of clinics where individuals who meet clinically significant levels of depressive symptomology based on self-report so they can be evaluated by mental health professionals. The target population is served by South Africa's public health system, where services are provided for free at point of service.

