**Eligibility Assessment, Enrollment, and Randomization.** The study staff will assess *eligibility*. Eligibility for parents and eligibility for adolescents will be individually determined. Eligibility will be auto-calculated using a pre-programmed computerized method using our secure mobile project-dedicated android phones or “survey devices” that are part of our field-based data collection system (see details on SurveyToGo software used for data collection). The survey devices will automatically calculate eligibility based on the inclusion/exclusion criteria outlined above. Final eligibility will be determined by dyadic eligibility (that is both parents and adolescents have to be eligible to be invited to participate in this family-based intervention). Eligible parent-adolescent dyads will be invited to participate in the baseline assessment and attend an enrollment session where randomization will occur. If interested, each individual in the dyad will be go through individualized informed consent and assent processes. After completing baseline data collection, each individual in the dyad will be issued matching “invitation tickets” to attend the enrollment session. Invitation tickets provide participants with date and location of the enrollment session. These invitation tickets also display unique ID numbers to allow us to verify at the enrollment session that we have screened individuals for eligibility (by matching unique ID numbers on the ticket with our data system) and help us ensure scheduling of dyads. Dyads will attend an enrollment session where trained study staff will answer questions about the study. Following this information session, study staff will gather voluntary informed consent and assent forms from interested individuals. If consent and assent are obtained for a complete dyad, trained study staff will use a computerized block randomization procedure using our FileMaker Software which automatically determines dyad assignment to the intervention or control group based on programming out [name] and our data team. The block randomization procedure will balance allocation dyads for adolescent gender. Dyads assigned to the intervention group will receive the first intervention session that same day. Dyads assigned to the control group will be given usual care (consisting of a packet of existing available brochures on HIV, STIs, mental health including places to access care). Because randomization occurs in a group setting, assignment is not concealed from participants or from study staff who are part of the intervention team or fidelity

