**Retention.** We gather information to help track and retain participants including: 1) at baseline, documenting multiple participant contact details (address, phone numbers), names and phones of three individuals who know how to contact the family; 2) monthly contact via telephone or text with reminders for upcoming appointments and to update contact information; 3) geo-

location data to facilitate in-home assessments in a context where homes often do not have addresses or street names. We will also provide participants with reminder cards with study staff contact details and timeframes (and if possible, exact dates), and locations for follow-up data collection. We will attempt to contact participants who are not available at home, for participation in follow-up data collection to either meet them at their home or utilize the telephone to complete data collection.

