## 5. Data Safety and Monitoring

**Data and Safety Monitoring Plan.** Overall internal monitoring of the safety of human subjects will be conducted by PIs. At eligibility screening, those identified with possible clinically significant levels of mental health will be a given list for their nearest mental health service, provided through South Africa's free public health service. This is because this is a prevention study – we offset risk by only including individuals with low levels of depressive symptoms. We screen out those who have progressed to clinically significant ranges. The PIs will oversee monitoring activities. For non-emergency issues, a weekly meeting will be held to address study progress, recruitment and retention, data collection, and other factors related to human subjects and meetings will be held more often if necessary. Emergency protocols will be developed to address serious adverse events and emergency ethical issues should these arise during the intervention or follow-up assessments. Staff will be trained in responses to potential adverse events and given protocol guidelines on how to address these situations. We provide these Standard Operating Protocols or SOPs for review. In cases of adverse events such as identification of depression, suicidal or homicidal ideation, staff will be trained to immediately contact the Project Manager to alert them of the situation. The Project Manager will consult with the PIs to address these issues who are on call at all times during active study recruitment, intervention testing, or assessment. Study staff will be instructed to inform participants they do not have to answer questions that they find too distressing and will be reminded that they can discontinue participation at any time. If needed, participants will be linked to services for stabilization and referral process if they decompensate during eligibility screening, intervention testing, or assessment procedures. Moreover, participants who report significant depression or suicide will not be enrolled in the study (per our exclusion criteria) and will be immediately referred for evaluation and if necessary, psychiatric admission at a local emergency department. Moreover, the Project Manager and PIs should be immediately notified. Participants who develop or report significant depression, suicidal, or homicidal risk during the course of experimental intervention or during assessments will be discontinued and immediately referred for evaluation for psychiatric admission at a local emergency department. All adverse events will be immediately reported to PIs. Serious adverse events will be reported to Brown University IRB/University of Cape Town HREC. A written report will also be given in writing to NIH. All ethical issues will be reported in an annual report to Brown University, University of Cape Town, and NIH.

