At eligibility screening, those identified with newly diagnosed HIV and STIs will be offered referral to care and treatment. This process will be repeated at 6- and 12-month follow-up time points. At eligibility screening, participants who report significant depression or suicide will not be enrolled in the study (per our exclusion criteria) and will be immediately referred for evaluation and if necessary, psychiatric admission at a local emergency department. Suicidal admission will result in immediate notification to the Project Manager and PIs. Participants who develop or report significant depression or suicidality during the course of experimental intervention or during assessments will be discontinued and immediately referred for evaluation. Those with clinically significant levels of depression will be given a list for their nearest mental health service (as defined by our reliable, valid symptom measure for depression) provided through South Africa's free public health service. This process will be repeated at 6- and 12-month follow-up time points. This is because this is a prevention study – we offset risk by only including individuals with depressive symptoms below the clinically significant range for depression. We screen out those who have progressed to clinically significant ranges for depression. Standard Operating Protocols have been developed to address serious adverse events and emergency ethical issues should these arise during the intervention or follow-up assessments (see Appendices). Staff will be trained in responses to potential adverse events and given protocol guidelines on how to address these situations. In cases of adverse events such as identification of depression, suicidal or homicidal ideation, staff will be trained to immediately contact the Project Manager to alert them of the situation. The Project Manager will consult with the PIs to address these issues who are on call at all times during active study recruitment, intervention testing, or assessment. Study staff will be instructed to inform participants they do not have to answer questions that they find too distressing and will be reminded that they can discontinue participation at any time. If needed, participants will be linked to services for stabilization and referral process if they decompensate during eligibility screening, intervention testing, or assessment procedures.

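### The rules that withdraw or discontinue adolescents for depression do not keep them in follow-up, so 12-month primary-outcome data can be lost because of depression status

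*Combined protocol and SAP*

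**What the plan says.** Three passages deal with adolescents whose mental state worsens after enrolment.

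- Part D, section 1 (Potential Risks and Discomforts to Participants), item 5, on psychological decompensation: "If this occurs, they will be withdrawn from our prevention focused trial". The object is the trial, not the intervention.
- Section 5 (Data Safety and Monitoring): "Participants who develop or report significant depression, suicidal, or homicidal risk during the course of experimental intervention or during assessments will be discontinued". It does not say what they are discontinued from.
- Part D, section 2 (Protection against Possible Risks), Data and Safety Monitoring Plan: "Participants who develop or report significant depression or suicidality during the course of experimental intervention or during assessments will be discontinued". Again the object is missing.

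The last passage continues: "Those with clinically significant levels of depression will be given a list for their nearest mental health service", and then "This process will be repeated at 6- and 12-month follow-up time points". The only numeric threshold, a CES-DC of 16 or more, is an entry exclusion under Inclusion and Exclusion Criteria. It is not given as a withdrawal trigger.

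The Retention paragraph covers contact details, reminders and tracing: "We will attempt to contact participants who are not available at home, for participation in follow-up data collection". It does not mention withdrawn or discontinued participants. The footnote that stretches the 12-month window and the COVID-19 text on out-of-window collection do not mention them either.

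For missing outcomes, the Sample Size paragraph allows 15% loss and treats loss as censoring. The Aim 1 analysis plan names GEE, two-sample tests and a Cox model, with no weighting or imputation.

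**The concern.** Onset of clinical depression is what the trial aims to prevent, and CES-DC is a primary outcome. A rule that ends participation because of depression makes missing data depend on an earlier value of that outcome.

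The words about assessments matter most. At the 6-month visit the sessions are over, and controls never had any: "Dyads assigned to the control group will be given usual care (consisting of a packet of existing available brochures". Discontinuation at that visit has no intervention left to stop. What it can still stop is follow-up.

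At stake are the 12-month CES-DC, the HIV/STI tests and the behaviour measures of the same adolescents. Their time to debut would be censored when depression is reported. The arms may also differ, because discontinuation during sessions can happen only in the intervention arm.

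**Working it through.** **Plan's own figure.** With 440 × 0.85 = 374 evaluable per arm, 30% v 40%, two-sided 0.05:

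power = Φ[(0.10 − 1.96·√(2·0.35·0.65/374)) / √((0.21 + 0.24)/374)] = Φ[(0.10 − 0.0684)/0.0347] = Φ(0.91) = 81.9%.

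Subtracting a continuity correction of 1/374 from the difference gives 79.8%. The stated 80% is reproduced.

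**Data loss alone.** The documents give no withdrawal rate. Suppose a further 5% or 10% of evaluable adolescents were lost equally in both arms, without bias. Then n = 355.3 or 336.6 per arm, and power for 30% v 40% is 79.9% or 77.8%. An acute-only rule would probably lose fewer.

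**Bias in CES-DC, assessment route.** Assumptions, none from the documents unless noted:
- normal scores, SD 6, 6-to-12-month correlation r = 0.5;
- true difference 0.21 × 6 = 1.26 points (1.23 is detectable with 80% power at 374 per arm);
- cut-off 15.5;
- control mean 7 (the pilot intervention arm at 3 months, so a low end), 9 or 12;
- exchangeable working correlation, because Model (1) has a person-level intercept; the plan does not state one.

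Suppose first that every 6-month score of 16+ leads to withdrawal. With a = (15.5 − μ)/6 and P = 1 − Φ(a), the mean standardised 6-month score of those left is m = −φ(a)/(1 − P). The completer mean at 12 months is μ + r·6·m. The GEE mean is μ + (r − α)·6·m, where α is the estimated working correlation.

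Example at control mean 9: a = 1.083 (control) and 1.293 (intervention), m = −0.258 and −0.192, α = 0.38. The completer difference is 1.26 − 3 × (0.258 − 0.192) = 1.06. The GEE difference is 1.21.

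| Control mean | Controls withdrawn | Completer t-test loses | GEE loses |
|---|---|---|---|
| 7 | 8% | 11% | 2% (0.03 points) |
| 9 | 14% | 16% | 4% (0.05 points) |
| 12 | 28% | 23% | 7% (0.09 points) |

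The standard error is 6·√(2/374) = 0.44. Over SD 4–8 and r 0.3–0.7, restricted to cases with at most 15% of controls withdrawn, GEE loses 0.1–5% and the t-test 2–23%. If half of those at 16+ are withdrawn, the base-case losses are 0.4–0.9% and 5–8%. If 16+ leads only to the clinic list, this source contributes nothing.

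**Does the every-16+ reading fit the plan?** The plan expects 25–35% of controls to have a lower score than at baseline. Take baseline as uniform on the integers 6–15 (mean 10.5, SD 2.87) and follow-up SD 6. A lower whole-number score means a difference below −0.5.
- Baseline correlation 0.5, 35% reduced: 10.0 + 0.385 × 5.20 = 12.0.
- Baseline correlation 0, 25% reduced: 10.0 + 0.674 × 6.65 = 14.5.

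At those control means P = 28% and 43%, against a 15% allowance for all loss. The reading does not fit.

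**Session route.** Suppose the most distressed 1% or 2% of the intervention arm are discontinued in sessions and lost to both visits. The shift is r·6·φ(q)/(1 − p), where q is the upper p quantile: 3 × 0.0267/0.99 = 0.08 points, or 3 × 0.0484/0.98 = 0.15 points. That inflates the benefit by 6% or 12% under either estimator, and by about half as much with baseline adjustment. These rates too are assumed.

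**The case against.** A reader might infer that every adolescent scoring 16 or more at 6 months is removed, and hence that the depression result is materially biased. The documents do not support that. The only explicit withdrawal from the trial is for decompensation. Section 5 groups depression with suicidal and homicidal risk and sends these participants for psychiatric admission assessment, which reads as an acute-risk rule. People at clinically significant levels get a clinic list, repeated at follow-up. The every-16+ reading also breaks the plan's own loss allowance. This part of the objection stands.

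It also stands that inference rests on the longitudinal GEE, where the bias is small; the larger percentages belong to completer t-tests. The normal model is rough for a score that cannot be negative: at mean 7 and SD 6, about 12% of it lies below zero. The operating procedures and consent forms are not in the public text and may say what discontinuation means.

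What does not fall away is the wording. The clinic-list sentence describes referral and does not promise continued follow-up. Item 5 gives the same list to people it has just withdrawn, so receiving the list does not imply staying in. The general wish to limit missing data is never applied to these participants.

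**Conclusion.** The point holds as a should-fix gap in a stated rule. Decompensated participants leave the trial, others are discontinued from something unnamed, and nothing visible keeps either group in follow-up. Primary-outcome data can therefore be lost because of depression status.

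The likely scope is acute cases. On that scope, the CES-DC bias under GEE should be small against a standard error of about 0.44 points. Its direction is unknown: removing more high-scoring controls at 6 months shrinks the difference, while session discontinuation inflates it. All bias figures rest on assumed SD, correlation, means and withdrawal rates. The 6-month comparison is untouched by withdrawals made at the 6-month visit. No bias was calculated for HIV/STI, behaviour or debut; for those the cost is lost data and early censoring. The case for change rests on avoidable loss and possible imbalance between arms, not on a demonstrated distortion of the result.

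**What to change.** Keep the referral and emergency procedures. Amend Part D, section 1, item 5 so that decompensation leads to withdrawal from the intervention. State in section 5 and in the Part D monitoring plan that discontinuation ends intervention sessions only. Offer all randomised adolescents the planned 6- and 12-month assessments, deferred while clinically unsafe, unless consent or assent is withdrawn, and analyse them as randomised. State that a follow-up CES-DC of 16+ on its own leads to the clinic list and not to withdrawal. Report discontinuations by arm, visit and trigger.

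For CES-DC values still missing, a likelihood-based mixed model, weighted GEE or multiple imputation is a secondary safeguard and needs no new data.

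The cost is an amendment to the protocol, consent forms and operating procedures, with ethics approval, and a few more visits of a kind already planned. Whether an acutely unwell minor should be assessed is also a clinical and ethical judgement, which is why the offer allows deferral.
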